β2 microglobulin (central)		X		X				X		
Salivary glands										
Lip biopsy (optional)								(X) ⁹		
Other										
Biocollection (blood: serum and plasma) (optional) (central)		(X)		(X)				(X)		
Biocollection (PBMC) (optional) (central)		(X)				(X)				
Biocollection (extracted RNA) (optional) (central)		(X)		(X)				(X)		

- For each patient, there will be a screening period between W -4 and W000. Patients who meet the eligibility criteria at screening will be admitted to inclusion visit (W000).
- The time windows that are given for the visits ($\pm 2d$ etc..) are given compared to W000
- Lip biopsy should not be performed before the sialometry
- Physical examination, vital signs and 12-lead ECG will be performed pre-dose

* The results of the examinations should be available at W000, to assess the inclusion criteria.

**Two follow-up visits will be scheduled for safety and PK/PD assessments: the first visit will be performed at W019, and the second visit at W028. Between visits, the patient will be able to contact the site in case of any problem. In case of premature IMP discontinuation, the FU visits will be performed 9 and 18 weeks after the last IMP administration, for safety assessments.

*** Schirmer, OSS and Sialometry can be performed within 2 days before the scheduled visit's date at W000 and W004. At W013 these tests can be performed in the time window allowed by the protocol (± 2 days).

One blood sample will be performed between W011 and W012 for PK assessment. The blood sample will be performed at site or not according to local facilities

One blood sample will be performed at W16 \pm 5 days for PK assessment. The blood sample will be performed at site or not according to local facilities

1 At W000 and W002, patients will be monitored closely for 2 hours after completion of IV. infusion (or longer, at the discretion of the Investigator) for vital signs, physical examination, and signs or symptoms of adverse events including development of an injection reaction. At all other visits with IMP administration, post dose assessments will similarly include assessing infusion site, physical examination and vital signs before dismissing the patient from the clinical site

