8.2. Methods and measurement times

- **Physical examination:** will be performed at ASSE, W000, W002, W004, W007, W010, W013, W019, W028.
- **Vital signs (pulse, blood pressure, body temperature):** will be assessed after 5 min rest, in supine position Blood pressure will be measured preferably on the same arm. All devices routinely used in the centre to measure blood pressure are accepted.

Vital. signs will be performed at ASSE, W000, W002, W004, W007, W010, W013, W019, W028.

On the days of administration, the physical examination and vital signs will be performed:

- pre-dose
- and post dose (before discharge): at W000 and W002, patients will be monitored closely for 2 hours after completion of IV infusion (or longer, at the discretion of the Investigator) for vital signs, and signs or symptoms of adverse events including development of an injection reaction. At all other visits with IMP administration (W004, W007, W010), post dose assessments will similarly include assessing infusion site, physical examination and vital signs before dismissing the patient from the clinical site.

- **Body weight (kg):** will be measured with an empty bladder, the patient being in indoor clothing, without shoes at ASSE, W000, W004, W010, W013, W019, W028.
- **12-lead ECG:** A standard 12 lead ECG will be recorded in lying position after 5-10 minutes rest. The investigator or designated physician will review and sign all ECGs. Once signed, the original ECG tracing will be retained with the patient's source documents. At the request of the Sponsor, a copy of the original ECG will be made available.

Clinically significant ECG abnormalities, as judged by the investigator, will be recorded on the relevant medical history CRF page prior to first dosing and on the Adverse Events page thereafter.

12-Lead ECG will be performed at W000, W004, W010, W013, W019, W028.

On the days of administration, the 12-lead ECG will be performed pre-dose.

- Laboratory examinations

Laboratory tests analysis will be subcontracted to a central laboratory except for assessments such as infectious disease panel, HBA1c, tuberculosis test and for ESR, cryoglobulins, urinalysis and pregnancy tests. The details for sampling, handling, storage and shipping of the samples will be described in a laboratory manual.

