8.3. Definition of Adverse events

An adverse event is defined as any untoward medical occurrence in a patient participating in a clinical study, whether or not there is a causal relationship with the IMP and/or experimental procedures, occurring or detected from the date the patient signs the information and consent form, irrespective of the period of the study (periods without administration of the IMP (e.g. run-in period) are also concerned).

An adverse event can therefore be:

- any unfavourable and unintended sign (including an abnormal finding from an additional examination such as lab tests, X-rays, ECG, ...) which is deemed clinically relevant by the investigator,
 - any symptom or disease,
 - any worsening during the study of a symptom or a disease already present when the patient entered the study (increase in frequency and/or intensity),
- and detected during a study visit or at an additional examination or occurred since the previous study visit.

Of note:

Any **hospitalisation for social reasons, educational purpose** (e.g. learning of diabetes management by the patient) or routine check-up should not be considered as an adverse event and should not be reported in the CRF.

The following procedures, whether planned before the study or not, whether leading to a hospitalisation or not, **should not be reported in the e-CRF and kept in the source data (or patient file):**

- Therapeutic procedures related to a non-aggravated medical history (e.g. cataract extraction not due to an aggravation of the cataract during the study, haemodialysis sessions related to a renal insufficiency not aggravated during the study),
- Prophylactic procedures (e.g. sterilisation, wisdom teeth removal),
- Comfort procedures (e.g. cosmetic surgery),
- Control procedures of a pre-existing condition without aggravation (e.g. colonoscopy to control the remission of colon cancer).

Symptoms related to the studied pathology (pSS):

Symptoms of pSS occurring prior to first dosing have not to be reported in the medical history page of e-CRF. Only aggravations or new occurrence of pSS symptoms from first dosing will be reported as adverse event. In case of major worsening of Primary Sjögren's syndrome, the patient could be prematurely withdrawn according to the judgement of the investigator. (see [Sections 5.6.1](#) and [8.9.2.4](#)).

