3. GENERAL STATISTICAL CONSIDERATIONS

3.1. Descriptive statistics

Descriptive statistics will be provided by treatment group, and all treatment groups pooled (for analyses on disposition of patients, baseline characteristics and patient follow-up, and on adverse events).

For **qualitative data**, number of observed values, number and percentage of patients per class will be presented. Unless otherwise specified in the TLG, no class "Missing" is considered.

For **quantitative data**, number of observed values, mean, standard deviation, median, first and third quartiles, minimum and maximum will be presented.

For **event data**, number of patients having experienced the event (n) and number of events that occurred (for AE analyses only) (NAE) will be presented.

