4.4. Safety analysis

All safety analyses will be performed by treatment group in the Safety Set, on the ASSE-W013 and ASSE-W028 periods.

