4.4.1. Adverse events

Definition:

- **Treatment Emergent Adverse Events (TEAE)** on the ASSE-W013 period are defined as all adverse events:

- Which occur between the infusion start date/time of the first IMP intake (included) and the date of W013 visit (included) or the last IMP intake date + 21 days (included) if the W013 visit has not been done

or

- Which occur before the infusion start date/time of the first IMP intake and which worsen (in terms of intensity) or become serious according to the investigator opinion between the infusion start date/time of the first IMP intake (included) and the date of W013 visit (included) or the last IMP intake date + 21 days (included) if the W013 visit has not been done.

Of note, in case of multiple information of the same event before the first IMP intake date, the information nearest to the first IMP intake date is taken into account.

- **Treatment Emergent Adverse Events (TEAE)** on the ASSE-W028 period are defined as all adverse events:

- Which occur between the infusion start date/time of the first IMP intake (included) and the last IMP intake date + 85 days (included),

or

- Which occur before the infusion start date/time of the first IMP intake and which worsen (in terms of intensity) or become serious according to the investigator opinion between the infusion start date/time of the first IMP intake date (included) and the last IMP intake date + 85 days (included).

Of note, in case of multiple information of the same event before the first IMP intake date, the information nearest to the first IMP intake date is taken into account.

Analysis:

Number of events, number and percentage of patients reporting at least one event, presented by primary system organ class, and/or preferred term (depending on the analysis), will be provided for:

- Serious adverse events (SAE) over the analysed period according to the investigator or sponsor opinion.
- Adverse events of special interest.
- Treatment Emergent Adverse Event (TEAE).
- TEAE leading to IMP withdrawal.
- TEAE requiring new treatment or increase of on-going treatment.
- TEAE requiring surgical or medical procedure.
- TEAE related to IMP.
- TEAE related to Pss.
- Serious TEAE.
- Serious TEAE related to IMP.
- TEAE of Grade 3-4 intensity.
- Non serious TEAE over the corresponding treatment period.

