TEAE will be described according to the seriousness, the intensity, the relationship with the IMP, the action taken regarding the IMP, the requirement of added therapy and the outcome. TEAE will also be described by time to onset according to the following classes: [0-4],]4,13] and > 13

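### SAP 4.4.1 shows TEAE counts by onset class for classes of unequal length, so a constant event rate gives about 2.25 to 2.3 times as many events in each later class as in the first

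*SAP*

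**What the plan says.** SAP 4.4.1 closes its list of adverse event summaries with: "TEAE will also be described by time to onset according to the following classes: [0-4],]4,13] and > 13". It gives neither a unit nor a time origin. The cut points coincide with visits W004 and W013, so weeks from first infusion is the natural reading.

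For event data, SAP 3.1 says that the "number of patients having experienced the event (n) and number of events that occurred (for AE analyses only) (NAE) will be presented". SAP 4.4.1 adds the percentage of patients. Neither section gives a denominator specific to an onset class or a rate per unit of time. The exposure summary in SAP 4.2.1 covers numbers of infusions and intervals between them, so it does not supply person-time either.

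SAP 4.4 applies the safety analyses to two periods: "All safety analyses will be performed by treatment group in the Safety Set, on the ASSE-W013 and ASSE-W028 periods". The TEAE window ends differently in each:
- For ASSE-W013 it ends at "the date of W013 visit (included) or the last IMP intake date + 21 days (included) if the W013 visit has not been done".
- For ASSE-W028 it ends at "the last IMP intake date + 85 days (included", whatever the date of the last follow-up visit.

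**The concern.** A table of onset by period is normally read to see whether events cluster soon after the first infusions or appear later. Protocol section 2 names risks of both kinds for close monitoring, among them acute hypersensitivity, cytokine release, infection and lymphopenia. If the classes differ in length and only counts are shown, the counts follow class length. A flat rate then looks like later onset, and an early excess looks smaller beside the later classes than it is.

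The last class raises a separate issue. Its end is tied to the last infusion, so a patient who stops early has less time in it, or none, but would stay in the denominator if percentages are taken over the whole Safety Set.

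**Working it through.** The documents give no figure for the onset classes, so there is nothing of their own to reproduce. The inputs are the class limits (SAP 4.4.1, read as weeks), infusions at W000, W002, W004, W007 and W010 (days 0, 14, 28, 49 and 70), and the two TEAE windows.

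**Class lengths, ASSE-W028, all five infusions given.** The window ends on day 70 + 85 = 155, or week 22.1.
- [0-4]: 28 days
- ]4,13]: 91 − 28 = 63 days
- >13: 155 − 91 = 64 days

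At a constant rate, expected events are proportional to length: 28/155 = 18.1%, 63/155 = 40.6%, 64/155 = 41.3%. The count ratios to the first class are 63/28 = 2.25 and 64/28 = 2.29. Divided by person-time, both become 1.00.

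**Early stopping.** SAP 4.3.1 assumes that all intercurrent events together stay below 10%, so 10% is taken as an upper bound for stopping. If stoppers contribute nothing after they stop, the ]4,13] to [0-4] ratio is:
- all stop just before week 4: 2.25 × 0.90 = 2.03
- stopping spread evenly over 13 weeks: 9 × (1 − 0.10 × 8.5/13) / [4 × (1 − 0.10 × 2/13)] = 2.14

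**Patients with at least one TEAE.** With weekly rate λ = −ln(1 − p)/13 for 13-week incidence p, the ratio is (1 − e^(−9λ)) / (1 − e^(−4λ)).

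| 13-week incidence | Ratio ]4,13] to [0-4] |
|---|---|
| 10% | 2.21 |
| 30% | 2.11 |
| 50% | 1.98 |
| 57.1% | 1.93 |
| 80% | 1.72 |

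The ratio equals 2 at λ = 0.0498, which is an incidence of 18% in the first class and 48% over 13 weeks. The 57.1% row uses the phase I figure in protocol section 2 (healthy volunteers, all groups combined) and is illustrative only. If each patient is classed by first onset alone, the ratio is (e^(−4λ) − e^(−13λ)) / (1 − e^(−4λ)). It falls below 2 once 13-week incidence exceeds 21%, and is 1.60 at 50%.

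**Time available in the >13 class, ASSE-W028.** Days = max(0, last infusion day + 85 − 91).

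| Last infusion | Days in >13 |
|---|---|
| W000 | 0 |
| W002 | 8 |
| W004 | 22 |
| W007 | 43 |
| W010 | 64 |

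For early stoppers, protocol 4.1.2 says: "In case of premature IMP discontinuation, the FU visits will be performed 9 and 18 weeks after the last IMP administration". Contact therefore continues, but the TEAE window closes 85 days after the last infusion.

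**ASSE-W013.** The window closes at the W013 visit (day 91, ±2 days) or 21 days after the last infusion (70 + 21 = 91). The >13 class then has about two days at most. The other two classes split 28/91 = 31% and 63/91 = 69%.

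**Visits.** The schedule can be seen in protocol 8.2, where the physical examination "will be performed at ASSE, W000, W002, W004, W007, W010, W013, W019, W028". The adverse event row of the protocol 4.1.2 table has the same post-baseline visits. Post-baseline visits per week are 2/4 = 0.50, 3/9 = 0.33, and 1/9.1 = 0.11 for the part of the last class inside the window. This pattern can only lower later counts. If capture were strictly per visit, the ratio of the second class to the first would be 3/2 = 1.5.

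**The case against.** The strongest reply is that this is a descriptive, untested table in a planned 45-patient phase IIa study. Its class limits are printed, and the classes follow the design: two-weekly dosing, three-weekly dosing, then follow-up. No decision criterion uses it. Adverse events of special interest have their own summaries, and haematology is described by visit. Disposition by visit and patients by number of infusions give some idea of numbers at risk. The table shells are in a separate document (SAP section 1) that is not available here and may state the unit and denominators. Rates in the placebo arm would be imprecise: 15 patients × 4 weeks = 60 person-weeks, so one event is 1.7 per 100 person-weeks. All of this stands, and it keeps the severity low. It does not make raw counts comparable across classes of 28, 63 and 64 days.

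A reader might infer three stronger things that the documents do not support:
- **That falling numbers at risk and sparser visits help to produce the rise.** They work against it, because both lower later counts. Capture is also not limited to visit days: protocol 8.3 includes events "and detected during a study visit or at an additional examination or occurred since the previous study visit".
- **That an event rate will appear to double.** The SAP plans no rate for these classes. It is the raw event count that more than doubles, and the number of patients affected rises by less.
- **That the comparison between arms is distorted.** Both arms share the same classes and schedule, so class length cancels. Only a difference in early stopping could matter, through the window tied to the last infusion. The protocol does provide for stopping after related adverse events, but no differential rate is given. That window applies to every ASSE-W028 TEAE table, not to this one alone.

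**Conclusion.** The point holds for reading onset timing across classes. In ASSE-W028, at a constant rate, each later class shows about 2.25 to 2.3 times the events of the first. For ]4,13] the ratio is about 2.0 to 2.1 if 10% stop early and contribute nothing afterwards. For patients with at least one TEAE it is lower, and below 2 at 13-week incidences above about 48%. The >13 class offers 0 to 64 days depending on the last infusion, and almost nothing in ASSE-W013, where a near-zero count carries no information.

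This rests on the unit being weeks from first infusion, a constant rate on and off treatment, and infusions given on schedule. The missing adjustment is established for the SAP text only. Severity is low: no efficacy or decision result depends on this table.

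**What to change.** In SAP 4.4.1:
1. State that onset is measured in weeks from the start of the first infusion.
2. For each class and arm, add patients at risk at the start of the class, person-weeks inside the TEAE window, and overall events per 100 person-weeks. Give these rates for all TEAEs together, not by system organ class or preferred term.
3. Base the percentage of patients with an event on those at risk at the start of the class.
4. Show the >13 class only for ASSE-W028.

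The dates needed are already collected, and SAP 7.1.2 states that all infusion dates are complete, so the cost is minor programming. The downside is a longer table, with imprecise rates in the small placebo arm.

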4.4.2. Clinical laboratory evaluation

4.4.2.1. Blood samplings for haematology, biochemistry and coagulation

For each laboratory parameter, the following analyses will be performed:

- Descriptive statistics on value at baseline, on value at each post-baseline visit under treatment, on last post-baseline value under treatment and on change from baseline to last post-baseline value under treatment. These analyses will be performed on both periods (ASSE-W013 and ASSE-W028) only for haematology parameters and on ASSE-W028 for other parameters.
- Number and percentage of patients with at least one high/low emergent abnormal value under treatment, according to the laboratory reference ranges and to the cut-offs for PCSA values.
- Laboratory parameters classified (number and percentage of patients in each class) according to these reference ranges and cut-offs and using shift tables from baseline to the worst (high and/or low) values under treatment.

Moreover, listings of patients with out-of-range or PCSA analysable values emergent under treatment and of non-analysable values excluded from analyses will be provided.

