No serious adverse events were reported. None of the subjects prematurely discontinued their participation in the study for safety issue. No remarkable differences or dose-dependent trend in AE incidence could be observed between the different S95011 doses and placebo or between IV and SC administration of S95011.

Overall, 36 (57.1%) subjects of the study, all treatment groups combined, experienced at least one Treatment Emergent Adverse Events (TEAE) and treatment-related TEAEs were reported in 19 (30.1%) subjects. The most frequently reported TEAEs were headache (in 20 [31.7%] subjects overall), nasopharyngitis (in 6 [9.5%] subjects overall) and diarrhoea (in 5 [7.9%] subjects overall). The most frequently reported treatment-related TEAE was headache (in 13 [20.6%] subjects, all treatment groups combined). There were no clinically significant abnormalities in vital signs, physical examination, laboratory data and ECG. No cytokine release (IFN γ , IL12p70, IL4, IL5, IL6, IL8, TNF α) has been observed following S95011 administration in healthy volunteers. Overall, the drug is considered to be safe in healthy volunteers.

Pharmacokinetics

No significant dose effect was observed on dose-normalized C_{max} in the single administration part (Part 1) (dose range: 1 mg/kg to 10 mg/kg). A more than dose-proportional increase in AUC_{last} was observed between doses 1 vs 4 mg/kg and 1 vs 10 mg/kg. Half life increased from 111 to 280 h over the dose range of 1 mg/kg to 10 mg/kg.

Relative bioavailability measured as C_{max} , AUC_{last} , and AUC_{tau} was about 10-13% after s.c. administration compared to IV. infusion as OSE-127.

After multiple IV. infusions of S95011 (Part 2) (one administration every 2 weeks (q2w) for 4 weeks), approximate dose proportionality for C_{max} and AUC_{last} was observed from 6 to 10 mg/kg. The accumulation ratio was about 1.5 for AUC_{tau} and about 1.25 for C_{max} .

Pharmacodynamics

CD127 receptors were saturated at the first sampling time after the end of infusion with RO $\geq 95\%$. CD127 RO AUEC increased with increasing single IV. doses from 0.02 mg/kg to 10 mg/kg and the median time of CD127 RO $>95\%$ (t_{abl}) and $>20\%$ (t_{Emin}) was longer for higher doses. The same trend was observed after multiple IV. doses. CD127 RO AUEC increased with increasing S95011 AUC_{last} and AUC_{tau} .

Overall, no clear impact on lymphocyte subsets and cytokines nor clinically relevant elevation of cytokines was observed.

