1.1.2. Endpoints

The primary efficacy endpoint is the change from baseline in ESSDAI total score to W013.

The secondary efficacy endpoints are:

- ESSDAI score by domain and total score at each visit (value & change).
- ESSPRI score by symptom and total score at each visit (value & change).
- Proportion of patients with ≥ 3 points, ≥ 5 points, ≥ 7 points of improvement from baseline in ESSDAI at each visit.
- Proportion of patients with ≥ 1 point, ≥ 2 points, ≥ 3 points of improvement from baseline in ESSPRI at each visit.
- Proportion of patients with ≥ 3 points of improvement in ESSDAI and with ≥ 1 point of improvement in ESSPRI from baseline at each visit.
- Proportion of patients with a STAR total score ≥ 5 at each visit (value).
- Proportion of patients with a CRESS total score ≥ 3 at each visit (value).
- Fatigue (MFI) by domain, quality of life (SF-36) for mental and physical domains, physician and patient's global assessment of the disease activity (NRS) at each visit (value and change).
- Tear gland function: Schirmer's test and in OSS on the most affected eye and for the mean of both eyes at each visit (value and change).
- Salivary gland function: unstimulated and stimulated salivary flow rate at each visit (value and change).

The other secondary endpoints are:

- **Safety:** The safety and tolerability assessed by incidence of adverse events (AEs), change over time in safety parameters (vital signs, biological laboratory) and incidence of abnormal safety parameters throughout the study.
- **Pharmacokinetics:** Pharmacokinetics of S95011 in serum samples:
 - Pre-dose (before the start of the IMP infusion) at W000, W002, W004, W007, and W010.
 - Right after the end of the IMP infusion and in the [1-3h] interval after the end of the IMP infusion at W000 and W010.
 - Between W011 and W012, and at W013, W016, W019 and W028.

CL2-95011-001 - Statistical Analysis Plan | VV-TMF-116033 | 2.0

- **Pharmacodynamics:** Receptor Occupancy (RO) of S95011 in blood samples:
 - Pre-dose (before the start of the infusion) at W000, W002, W004, W007 and W010.
 - Right after the end of the infusion of the IMP at W000 and W010.
 - At W013, W019, W028.
- **Incidence of ADA** in serum samples:
 - Pre-dose (before the start of the infusion) at W000, W002, W004, W007 and W010.
 - At W013, W019, W028.

The exploratory endpoints are:

- **In blood:**
 - Lymphocytes subsets (PBMC) assessed at W000, W004, W007, W013.

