3.2. General definitions

Patients having taken at least one dose of IMP correspond to patients with at least one date of first and/or last IMP intake complete or partially complete.

Analysable value will be defined as any non-missing value, except for:

- Laboratory parameters:
 - A laboratory value is considered as analysable if non-missing and not flagged in the ClinTrial database as "not analysable".
 - Vital signs value is considered as analysable if collected under appropriate circumstances (corresponds to the item of the source database).

Baseline value will be defined as the last analysable value prior to the first IMP intake. In case of patient included and/or randomised but not having taken at least one dosage of IMP: value at baseline is defined as the last analysable value prior or equal to date of inclusion visit.

Considered periods are:

- ASSE-W013 period.
- ASSE-W028 period.

Last post-baseline value under treatment of the period will be defined as the last post-baseline analysable value under treatment during the considered period.

Change from baseline to post-baseline visit is calculated as: Value at the post-baseline visit - Value at baseline.

Change from baseline to post-baseline visit under treatment is calculated as: Value at the post-baseline visit under treatment - Value at baseline.

Change from baseline to last post-baseline value under treatment is calculated as: Last post-baseline value under treatment - Value at baseline.

For safety endpoints (except adverse events), the following definition will be applied:

- **High emergent abnormal value under treatment according to the laboratory reference ranges** is defined as value \leq ULN (Upper Limit of Normal laboratory reference range) or missing at the baseline of the treatment period and $>$ ULN under treatment.
- **Low emergent abnormal value under treatment according to the laboratory reference ranges** is defined as value \geq LLN (Lower Limit of Normal laboratory reference range) or missing at baseline of the treatment period and $<$ LLN under treatment.

- **High emergent abnormal value under treatment according to the cut-offs for PCSA** values is defined as value \leq ULS (Upper Limit used to define potentially clinically Significant abnormal values) or missing at baseline of the treatment period and $>$ ULS under treatment.

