7.1.1. Value prior to treatment / under treatment

Table (7.1.1) 1 - Definition of value prior to treatment

General definition	
For assessments without time collected Corresponding assessment date \leq date of the first IMP intake + X1 _{sup} days	X1 _{sup} = 0
For assessments with time collected Corresponding assessment date/time \leq infusion start date/time of the first IMP intake + X1 _{sup} days	
Specific definition	
For ESSDAI, ClinESSDAI and PhGA Corresponding assessment date = date of visit at W000 \leq date of the first IMP intake + X1 _{sup} days	
For ESSPRI, MFI, PGA, SF-36 Corresponding assessment date = date of visit at W000 \leq date of the first IMP intake + X1 _{sup} days	

Table (7.1.1) 2 - Definition of value under treatment

General definition	
For assessments without time collected	
On W000-W013 Period if W013 visit done Date of first IMP intake + X1 _{sup} ^(*) days \leq Corresponding assessment date \leq Date of W013 visit + X2 _{sup} days	X2 _{sup} = 0
On W000-W013 Period if W013 visit not done Date of first IMP intake + X1 _{sup} ^(*) days \leq Corresponding assessment date \leq Date of last IMP intake on the W000-W013 period + X2 _{sup} days	X2 _{sup} = 21
On W000-W028 Period Date of first IMP intake + X1 _{sup} ^(*) days \leq Corresponding assessment date \leq Date of last IMP intake on the W000-W028 period + X2 _{sup} days	X2 _{sup} = 85
For assessments with time collected	
On W000-W013 Period if W013 visit done Infusion start date/time of the first IMP intake + X1 _{sup} ^(*) days \leq Corresponding assessment date/time \leq Date of W013 visit + X2 _{sup} days	X2 _{sup} = 0
On W000-W013 Period if W013 visit not done Infusion start date/time of the first IMP intake + X1 _{sup} ^(*) days \leq Corresponding assessment date/time \leq Date of last IMP intake on the W000-W013 period + X2 _{sup} days	X2 _{sup} = 21
On W000-W028 Period Infusion start date/time of the first IMP intake + X1 _{sup} ^(*) days \leq Corresponding assessment date/time \leq Date of last IMP intake on the W000-W028 period + X2 _{sup} days	X2 _{sup} = 85

^(*) cf. definition of value prior to treatment.

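### For biochemistry and coagulation, the only numeric change from baseline in the SAP is normally to W019, nine weeks after the last infusion; none is planned to W013 or to a dosing visit

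*SAP*

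**What the plan says.** SAP 4.4.2.1 opens with a bullet of numeric summaries for each laboratory parameter. It begins "Descriptive statistics on value at baseline, on value at each post-baseline visit under treatment" and ends "on last post-baseline value under treatment and on change from baseline to last post-baseline value under treatment". Change by visit is not listed. The bullet closes with the period rule: "These analyses will be performed on both periods (ASSE-W013 and ASSE-W028) only for haematology parameters and on ASSE-W028 for other parameters".

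Two definitions fix which sample counts as last. SAP 3.2 states: "Last post-baseline value under treatment of the period will be defined as the last post-baseline analysable value under treatment during the considered period". In SAP 7.1.1, Table (7.1.1) 2, the under-treatment window on the longer period ends 85 days after the "Date of last IMP intake on the W000-W028 period". On the shorter period it ends at the W013 visit, or 21 days after the last infusion if that visit was not done.

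The other two bullets of 4.4.2.1, on emergent abnormal values and on shifts from baseline to the worst value, carry no period rule. The default in SAP 4.4, both periods, therefore applies to them.

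The safety endpoint in SAP 1.1.2 includes "change over time in safety parameters (vital signs, biological laboratory").

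**The concern.** The label under treatment suggests a change measured during exposure. For biochemistry and coagulation, the period rule moves that change into follow-up. If a drug effect on ALT, bilirubin, creatinine, CK, lipase, PT or aPTT appeared during dosing and had reversed by W019, the one numeric change statistic would sit near zero in both arms.

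There is also a timing problem. Protocol 10.1 and SAP 1 make ASSE-W013 the main analysis, with later data described afterwards. Because the whole first bullet is confined to ASSE-W028 for these parameters, even their by-visit values are not planned for the main analysis.

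The restriction is not explained. Protocol 10.1.2.5.2 lists the same numeric summaries for every laboratory parameter without it, and SAP 6 does not record it as a change. Elsewhere the SAP does more: haematology gets the summaries on both periods, and vital signs get change at each visit (SAP 4.4.3.1).

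**Working it through.** The plan gives no figure of its own to reproduce here. The check is date arithmetic, counting W000 as day 0.

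**Inputs**
- Last infusion: W010, ±2 days (Protocol 4.1.2 and 6.2).
- Biochemistry and coagulation samples after W010: W013 ±2 days, W019 ±7 days, W028 ±7 days (Protocol 4.1.2 and 8.2).
- Follow-up after early discontinuation: 9 and 18 weeks after the last infusion (Protocol 4.1.2 and 5.6.1).
- End of window on ASSE-W028: last infusion + 85 days (SAP 7.1.1).

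**Step 1: where the window closes.** W010 = 7 × 10 = day 70, and 70 + 85 = day 155, which is week 155 / 7 = 22.1.

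**Step 2: days from last infusion to each visit.** Nominal = visit day − 70. The shortest interval pairs the earliest visit with a day-72 infusion; the longest pairs the latest visit with a day-68 infusion.

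| Visit | Nominal | Shortest | Longest | Within 85 days? |
|---|---|---|---|---|
| W013 | 91 − 70 = 21 | 89 − 72 = 17 | 93 − 68 = 25 | always |
| W019 | 133 − 70 = 63 | 126 − 72 = 54 | 140 − 68 = 72 | always |
| W028 | 196 − 70 = 126 | 189 − 72 = 117 | 203 − 68 = 135 | never |

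For early stoppers, 9 weeks = 63 days is inside and 18 weeks = 126 days is outside.

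**Step 3: which value is last.** On ASSE-W028 it is W019 or the 9-week visit. There are two exceptions: that sample is missing, or an unscheduled sample or retest follows it before the window closes (SAP 7.2.3.2 counts these outside the by-visit summaries). Run on ASSE-W013, the last value would normally be W013, 21 days after the last infusion instead of 63.

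**Step 4: what the remaining outputs supply.**
- *Values by visit* allow a difference between the visit mean and the baseline mean to be read off, with whatever mismatch of patients missing samples create. They do not give the SD of within-patient change. With equal SDs at the two times and correlation r, SD of change = SD of values × √(2(1 − r)). The documents give no r. If r is assumed to lie between 0.5 and 0.9, the multiplier runs from √1.0 = 1.0 to √0.2 = 0.45, and the planned tables do not settle it.
- *Emergent counts and shift tables* are judged against each patient's own baseline and also run on ASSE-W013. They register only movement across a reference limit or a cut-off for potentially clinically significant values, so a shift in level that stays within a limit is not seen.

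**The case against.** A reader might infer that on-treatment change is never summarised for these parameters. The documents do not support that. Values at W002, W004, W007, W010 and W013 are tabulated beside baseline. Emergent abnormalities and baseline-to-worst shifts are patient-level comparisons by arm, take in unscheduled samples, and run on ASSE-W013 by default. A reversible effect large enough to cross a limit would appear there. One that shifted the mean without crossing a limit could be read from the by-visit means.

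A reader might also infer that the change is measured off drug. The protocol's "Half life increased from 111 to 280 h over the dose range of 1 mg/kg to 10 mg/kg" makes 63 days equal to 63 × 24 / 280 = 5.4 half-lives at the longest value, but that comes from single doses in healthy volunteers. With a half-life of 17 days (an assumption, 85 / 5) it would be 63 / 17 = 3.7. The protocol judges loss of effect by receptor occupancy and predicts it at W028, with no prediction for W019. What can be said is that W019 is well after dosing has ended.

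Other arguments for leaving the plan alone have some force:
- Lymphopenia is an adverse event of special interest, which could explain the extra haematology output.
- Phase I showed no clinically significant laboratory abnormality.
- These are descriptive tables in a 45-patient trial, and the efficacy criteria do not use them. Individual results are reviewed by the investigator, and a DSMB reviews safety data.
- The protocol itself plans laboratory change only to the last value, so change by visit goes beyond it.

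These points limit the seriousness. They do not explain why biochemistry and coagulation lack the ASSE-W013 summaries.

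**Conclusion.** The point holds as a gap in the table specification. For biochemistry and coagulation, no numeric within-patient change to W013 or to a dosing visit is planned. The one change statistic is normally taken 63 days after the last infusion (54 to 72 with visit tolerances), where an ASSE-W013 run would take it at 21 days (17 to 25). The main analysis also has no numeric summaries for these parameters, and SAP 6 does not record the restriction.

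This rests on visits falling within their windows, on no later unscheduled sample displacing W019, and on reading the unrestricted bullets under the SAP 4.4 default. If that default were not meant to apply, the gap would be wider. What is lost is the mean and SD of within-patient change, and with them a clear view of shifts that stay within limits. The primary efficacy analysis is unaffected. The change is worth making because it is cheap.

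**What to change.** In SAP 4.4.2.1, replace the period sentence so that the first-bullet summaries run on both ASSE-W013 and ASSE-W028 for all haematology, biochemistry and coagulation parameters, with ASSE-W028 serving as the follow-up summary. If any period restriction is kept, list it in SAP 6 with its reason. Change from baseline at each visit, as already planned for vital signs, would be a useful but optional addition.

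The samples are already taken at every visit concerned, and the ASSE-W013 output already exists for haematology. The cost is one sentence and a longer table package.
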